To provide conservative power estimates for our rare variant analysis, we performed a simulation study where DNA sequencing data were generated with the FREGENE package (18), which creates simulated data for realistic specifications of selection, recombination, migration and population structure. We simulated case-control status with disease prevalence set at 10%. With our proposed two-stage strategy of whole genome sequencing in 1334 subjects (corresponding to 667 emphysema or airway-predominant cases vs. 667 controls) and follow-up sequencing in 8000 subjects, we randomly selected a sliding window region with 20 rare variants (i.e., MAF < 0.01). Affection status was independently caused by a varying percentage of disease susceptibility loci (DSL) in the 20 regional rare SNPs within a sliding window. The disease model assumes that the odds of disease are additive for each risk allele on the log scale. To avoid overestimating statistical power, the association between the rare variants and affection status is assessed based on the Ionita-Laza approach across the two stages. **Table 1** shows the estimated power for a variety of scenarios with different odds ratios and varying number of DSLs (1-20 DSLs out of 20 rare variants) in the entire study population. All estimates are based on 1000 replicates. With odds ratios of 2.25, power will be excellent, even if there is substantial allelic heterogeneity. Rare variant analysis using the Exome Chip in the entire study population will have even greater power, with 96% power to detect an odds ratio of 2.0 with 60% of the SNPs in the region as DSLs.

Table 1: Power to Detect Rare Variant Associations within COPDGene

Odd Ratio for Disease Susceptibility Locus	% of SNPs in Region That Are Disease Susceptibility Loci				
	100	80	60	40	20
2.5	100	100	100	100	100
2.25	100	100	98	95	78
2.0	99	94	79	32	9

Risks and Discomforts

For the research procedures that are described in this protocol the major risk associated with the study is inadvertent breach of confidentiality with disclosure of health information linked to subject identifiers. With storage of social security numbers there is also the potential for financial impacts and identity theft if social security numbers are inadvertently lost or disclosed.

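### Table 1 covers 4 to 20 causal loci per 20-variant window, not the stated 1 to 20, and the conclusion on power at an odds ratio of 2.25 has no matching lower limit

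*Protocol*

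**What the plan says.** All of this stands in the Protocol, section Biostatistical Analysis, in the paragraph on the rare-variant power simulation and in Table 1 below it.

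- Window size: "we randomly selected a sliding window region with 20 rare variants (i.e., MAF < 0.01".
- Range that Table 1 is said to cover: a "varying number of DSLs (1-20 DSLs out of 20 rare variants) in the entire study population".
- What the columns measure: the percentage "of SNPs in Region That Are Disease Susceptibility Loci", with the values 100, 80, 60, 40 and 20.
- Rows at issue (odds ratio first, then power in % from the 100% column to the 20% column): "2.25 100 100 98 95 78" and "2.0 99 94 79 32 9".
- Conclusion: "With odds ratios of 2.25, power will be excellent, even if there is substantial allelic heterogeneity".

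The same paragraph presents the estimates as conservative and gives 1000 replicates per estimate. The section also makes windows of 20 SNPs the unit of analysis for the whole genome sequencing data, so the simulation describes an analysis that is actually planned.

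**The concern.** The sentence that states the range has Table 1 as its subject, so the range should match the columns. It does not: the three smallest numbers of causal loci are missing, and these are the least favourable ones. If they were simulated, their results were left out; if they were not, the range is wrong. The text needs correcting either way.

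The sentence that follows sums up the row for an odds ratio of 2.25 with a single adjective and no lower limit on the number of causal loci. Table 1 is the only tabulated power support for the two-stage sequencing strategy. Someone who takes the range and the conclusion together could believe that power had been shown to be high down to a single causal variant, when nothing was reported below four.

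**Working it through.** **1. Columns to loci.** Number of DSLs = percentage × 20 variants.

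| Column | DSLs | Power at OR 2.25 | Power at OR 2.0 |
|---|---|---|---|
| 100% | 20 | 100 | 99 |
| 80% | 16 | 100 | 94 |
| 60% | 12 | 98 | 79 |
| 40% | 8 | 95 | 32 |
| 20% | 4 | 78 | 9 |

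The table spans 4 to 20 DSLs. One, two and three DSLs would be columns of 5, 10 and 15% (1/20, 2/20, 3/20), and none is printed. Each row has five values under five headings, so no column appears to have been lost in reading the table.

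**2. What follows with little assumption.** In both rows power never rises as the number of causal loci falls. From 8 to 4 DSLs it drops by 95 − 78 = 17 points at OR 2.25 and by 32 − 9 = 23 points at OR 2.0. If the pattern continues, power for 1 to 3 DSLs is at most 78% at OR 2.25 and at most 9% at OR 2.0. The simulation error of the 78% cell is √(0.78 × 0.22 / 1000) = 0.013, or 1.3 points, so the fall from 95% is not noise.

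**3. Illustration only.** Suppose each causal locus is detected independently, and calibrate to the 78% cell. Then power with k DSLs is 1 − (1 − 0.78)^(k/4).

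- k = 1: 1 − 0.22^0.25 = 31.5%
- k = 2: 1 − 0.22^0.50 = 53.1%
- k = 3: 1 − 0.22^0.75 = 67.9%

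Check on the rest of the OR 2.25 row: for 8, 12, 16 and 20 DSLs the model gives 95.2, 98.9, 99.8 and 99.9%, against 95, 98, 100 and 100 printed. That fits.

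Check on the OR 2.0 row, calibrated to its 9% cell with 1 − 0.91^(k/4): the model gives 17, 25, 31 and 38%, against 32, 79, 94 and 99 printed. That does not fit.

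**4. How far other extrapolations spread (OR 2.25).**

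- Straight line through the 4- and 8-DSL cells: slope 17/4 = 4.25 points per locus, so 78 − 3 × 4.25 = 65% at 1 DSL and 78 − 4.25 = 74% at 3. The same line gives 78 − 17 = 61% with no causal locus at all, which is implausible.
- Normal test statistic calibrated to 78% at 4 DSLs, mean shift proportional to k, two-sided alpha 5 × 10⁻⁸: the shift at 4 DSLs is 5.451 + 0.772 = 6.223. At 3 DSLs, Φ(0.75 × 6.223 − 5.451) = Φ(−0.784) = 22%. At 1 DSL it is about 0%.

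The models tried give about 0 to 65% at 1 DSL and 22 to 74% at 3. The paragraph does not state the significance level, the distribution of allele frequencies below 0.01, or the split of cases and controls in the "follow-up sequencing in 8000 subjects". The missing cells therefore cannot be recomputed from the protocol.

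**The case against.** The strongest reply is that this is a slip of wording next to a table that corrects it. The columns are labelled in percent, the lowest is visibly 20%, and the 78% and 9% cells are printed. A careful reader is not misled about what was tabulated, and nothing in the section uses Table 1 to interpret windows without a signal. That limits the harm, but the text and the table still disagree, and the text errs in the favourable direction.

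Two stronger readings are tempting, and the documents support neither.

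- A reader might infer that the protocol claims excellent power specifically for 1 to 3 DSLs. The conclusion names no number of loci. Allelic heterogeneity commonly means several different causal alleles, and a window with one DSL would have none. If it means causal variants mixed with neutral ones, 20 or 40% causal may already count as substantial. What can be said is that the sentence sets no lower limit, right after a range that starts at 1.
- A reader might infer that power for 1 to 3 DSLs is at most about 30 to 68%. That is an extrapolation and not a bound. The independence model behind it fails on the OR 2.0 row, and other extrapolations give both lower and higher values. Only the ceiling of 78% rests on monotonicity alone.

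Whether 78% deserves the word excellent is a matter of taste, and the point does not depend on it.

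**Conclusion.** The mismatch is certain: the text claims 1 to 20 DSLs and the table shows 4 to 20. It follows that the conclusion for an odds ratio of 2.25 is broader than its evidence, which is at least 95% power with 8 or more DSLs, 78% with 4, and nothing below that.

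For 1 to 3 DSLs, power can be expected to be no higher than 78% at OR 2.25 and 9% at OR 2.0. This assumes only that power does not rise when fewer variants are causal. The values of about 32, 53 and 68% at OR 2.25 show what independent detection would imply; they are not estimates of what the protocol's simulation would give.

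The point takes the printed cells as correct. It should be put right because Table 1 carries the tabulated power case for a planned analysis, but it does not put the design in doubt.

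**What to change.** Do one of the following:

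1. Rerun the existing simulation at 1, 2 and 3 DSLs and add columns for 5, 10 and 15% to Table 1; or
2. change the stated range to 4 to 20 DSLs out of 20.

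In either case limit the conclusion to what was computed. If the table stays as it is, the sentence could say that, at an odds ratio of 2.25, power is at least 95% when 8 or more of the 20 variants are DSLs and 78% when 4 are, and that power for 1 to 3 DSLs was not tabulated and is expected to be lower. No specific figure for 1 to 3 DSLs should be inserted unless it has been simulated.

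The cost is a change of wording, or three more columns from an existing simulation. Enrolment, sequencing and study procedures are unaffected. The stated power becomes slightly less favourable at the low end.

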- a. Five years after the initial clinical evaluation, a second visit will be performed in all subjects enrolled in the study to assess disease status based on clinical, physiological, and chest CT assessments similar to the initial study visit.
- b. The cohort will also continue to be followed longitudinally with telephone questionnaires every six months to determine mortality, COPD exacerbations, current cigarette smoking and co-morbid disease events.

Subject Selection

We are recruiting up to 12,000 smoking and non-smoking subjects.

Subject Inclusion/Exclusion Criteria for Phase 1 Data

A total of 12,000 non-Hispanic White and African-American subjects will be or have been recruited. Data from the Phase 1 study visit has been stored in the Data Coordinating Center. Biological specimens have been stored at the Johns Hopkins Biorepository and at the Brigham and Women's Hospital Biorepository. CT images have been stored in the National Jewish Imaging Core as well as the Brigham and Women's Hospital and University of Iowa Imaging Cores.

Phase 1 Actual Enrollment:

Phase 1, which was performed from November 2007 until July 2012, enrolled 10,364 subjects. Of these subjects 3416 were African American and 6884 were Non-Hispanic White. Enrolled subjects classified by severity of lung disease were as follows:

- Smoker Controls – 4388
- GOLD 2 - 4 Subjects – 3690
- GOLD Unclassified – 1257
- GOLD 1 Subjects – 794
- Non-smokers controls – 108
- Lack final GOLD classification due to failed spirometry – 63
- Significant ILD noted on CT scan, excluded from analysis – 64

Inclusion Criteria for the COPDGene Central Study Protocol:

Enrollment in the COPDGene study at any of the twenty one clinical centers with subject identifiers and protected health information uploaded to the Data Coordinating Center.

Exclusion Criteria:

None, if the inclusion criterion is met

Enrollment of up to a total of 1700 additional non-smoker controls is anticipated in Phase 2.

Study Procedures Related to COPDGene Central Study Components

During the Phase 2 research study visit, the following procedures will be performed at the local Clinical Centers but are related to Central Study functions. Local Clinical Center functions are described to provide a context for the Central Study functions.

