This is an observational longitudinal investigation without a therapeutic intervention. It is expected that there will be deaths in both control and COPD subjects enrolled in this study that are not related to study procedures. It is expected that there will be hospitalizations from a variety of causes not related to study procedures including but not limited to newly discovered disorders, acute disorders requiring surgery, pre-existing conditions, and exacerbations of underlying COPD. Subjects may expire due to pre-existing or new diseases including cancer, cardiovascular conditions and COPD. These are anticipated events that are not related to this investigation. These events will not be prospectively collected as part of the current study and thus will not be reported to IRBs. There are no expected Serious Adverse Events in this study related to study procedures. At each Clinical Center, subjects will be observed for the development of tremulousness, and nervousness following bronchodilator medication. Unexpected Adverse Events related to study procedures will be reported to the IRB of the Clinical Center and to the Executive Committee. An Observational Safety and Monitoring Board (OSMB) has been appointed by the National Heart, Lung, and Blood Institute and will continue to oversee this study.

Quality assurance of spirometry data will be insured by the Pulmonary Function Core, which will review spirometry data from each study participant. Quality assurance of CT scans will be analyzed by the Imaging Core in Denver. Questionnaires and other data will be quality controlled by the Data Coordinating Center in Denver.

As noted above we anticipate that some subjects may expire during the next phase of this study due to a combination of pre-existing disease and the onset of new conditions. These events are not anticipated to be related to the study visit; however, they provide important information about the natural history of COPD and other smoking-related conditions. We will monitor and collect information about deaths in the cohort but will not report them to IRBs as study-related events unless they occur during a study visit or within twenty-four hours of the study visit and are judged to be related to a study procedure.

References

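### Two sentences in Monitoring and Quality Assurance give opposite instructions on IRB reporting of a procedure-related death that occurs more than 24 hours after a visit

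*Protocol*

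**What the plan says.** All the reporting text is in the Protocol, section Monitoring and Quality Assurance.

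- **Adverse-event rule (first paragraph).** "Unexpected Adverse Events related to study procedures will be reported to the IRB of the Clinical Center and to the Executive Committee". No time window is attached, and deaths are not carved out.
- **Expectedness (same paragraph).** "There are no expected Serious Adverse Events in this study related to study procedures".
- **Death rule (last paragraph).** The study undertakes to collect deaths: "We will monitor and collect information about deaths in the cohort". It then adds that it "will not report them to IRBs as study-related events unless they occur during a study visit or within twenty-four hours of the study visit". A second condition is joined to the timing, so that reportable deaths are those that meet it "and are judged to be related to a study procedure".
- **Oversight board.** The Observational Safety and Monitoring Board (OSMB) is mentioned once, as a body that "has been appointed by the National Heart, Lung, and Blood Institute and will continue to oversee this study". Neither rule names it as a recipient.

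Elsewhere, Specific Aim 4 provides for mortality follow-up: "The cohort will also continue to be followed longitudinally with telephone questionnaires every six months to determine mortality". The Mortality Assessment section describes how death records are gathered and adjudicated.

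**The concern.** Both rules address the same recipient, the IRB, and both can apply to the same event. The adverse-event rule turns on relatedness and unexpectedness. The death rule adds a condition on timing and joins it to relatedness, so that a site's judgement of relatedness is not enough by itself once the window has closed.

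The death most in need of a clear rule is one the site believes a study procedure caused. If it falls after 24 hours, a coordinator can cite the Protocol for reporting it or for not reporting it. The visits take place at 21 clinical centers under local IRBs, so two centers could handle the same kind of event differently and both be following the text. What is at stake is consistent safety reporting. No estimate or analysis of the study depends on it.

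**Working it through.** There is no sample size, power or error rate to reproduce. The check is to apply each rule to each kind of death and compare the instructions.

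**Step 1. Does a procedure-related death come under the adverse-event rule?** That rule covers events that are unexpected and related. The section states that no procedure-related serious events are expected, so any procedure-related death is unexpected. The same paragraph does call deaths in the cohort anticipated, but only as events unrelated to the study. A death judged related is therefore covered.

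**Step 2. How can the death rule be grouped?** Two readings are possible:

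- G1: (during the visit or within 24 hours) and related.
- G2: during the visit, or (within 24 hours and related).

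**Step 3. Compare the IRB instructions.**

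| Death | Adverse-event rule | Death rule, G1 | Death rule, G2 |
|---|---|---|---|
| Related, during the visit | Report | Report | Report |
| Related, after the visit but within 24 h | Report | Report | Report |
| Related, after 24 h | Report | Do not report | Do not report |
| Unrelated, during the visit | Not covered | Do not report | Report |
| Unrelated, after the visit | Not covered | Do not report | Do not report |

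The rules conflict in one row: related, after 24 hours. They do so under both groupings. G1 and G2 differ only for an unrelated death during the visit, which does not bear on this point.

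**Step 4. What work does the time limit do?** For any death after the visit, the death rule already withholds an IRB report when the death is unrelated, whatever its timing. So after the visit the 24-hour limit has one effect: it removes related deaths that come later. Those are the deaths the adverse-event rule sends to the IRB.

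**Step 5. What is left untouched?**

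- The death rule speaks of IRBs only. The Executive Committee leg of the adverse-event rule stands for a related death at any time.
- Deaths are collected and adjudicated whether or not they are reported. The first paragraph says that anticipated events, deaths among them, will not be prospectively collected. Taken with the last paragraph, Specific Aim 4 and Mortality Assessment, however, the Protocol clearly intends to follow deaths.
- Adjudication does not stand in for the IRB report. As described under Mortality Assessment, it assigns a cause (respiratory, cardiovascular, cancer or other) and has no category for relatedness to a procedure.

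**The case against.** The strongest reply is that the last paragraph is about background mortality. It refers back to the earlier discussion, speaks of deaths from existing or new disease, and says these are not expected to be connected with the visit. On that reading, related deaths stay wholly under the adverse-event rule and nothing conflicts. This explains how the sentence may have come about, but the text does not support it. The sentence governs deaths in the cohort generally and contains its own relatedness test, which would have no purpose if related deaths lay outside it.

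A second reply is that this is the central protocol and that centers work under locally approved protocols, which may set their own reporting rules. That lessens the practical effect. It does not remove the conflict, because the Study Design section says this document also covers procedures at the clinical centers.

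A third reply is that the study is observational and such a death should be rare. That stands, and it limits the importance of the point.

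A reader might also infer more than the document supports:

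- **That sites cannot learn of a death in time because contact is six-monthly.** The 24-hour window governs when a death occurs, not when the site hears of it. A related death inside the window that is discovered months later is still reportable.
- **That comparing the one-day window with the contact interval, or counting subjects with severe disease, sizes the problem.** Neither does. The first compares unrelated quantities, and the second counts Phase 1 enrolment, not related deaths.
- **That a safety signal would be lost.** The Executive Committee route and the collection of deaths both remain.
- **That the OSMB is excluded.** It is merely not named as a recipient. A board charter that is not shown may settle what it receives.

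**Conclusion.** The internal contradiction is real and confined to one case: for a death judged related to a study procedure and occurring after 24 hours, one sentence requires an IRB report and the other rules it out. This rests on the wording alone and on one inference, that a procedure-related death is unexpected because the section says no procedure-related serious events are expected. It does not depend on how the or/and clause is parsed.

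The size cannot be put as a number, since the document gives no basis for an expected count of such deaths. It should be treated as a low-frequency drafting fault with a serious event behind it. The absence of the OSMB from both rules is an omission of secondary interest and not part of the contradiction.

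**What to change.** Amend Monitoring and Quality Assurance so that a single rule governs IRB reporting of procedure-related deaths. One way is to add to the closing sentence that its 24-hour condition does not remove a death judged related to a study procedure from the related-adverse-event rule. While the sentence is open, its or/and clause could be regrouped so that only one reading is possible.

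Optionally, state whether related-event reports also go to the OSMB, or refer to the document that says so.

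The cost is one or two sentences in a protocol amendment, and at most an occasional additional IRB report. No procedure, visit, data item or member of staff is added.

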Appendix I. Data Sharing and Access Policy

September 15, 2014

Genetic, Imaging and Phenotype Data on the COPD Gene Cohort

Access to and use of the COPD Gene data requires protection of the confidentiality of the subjects and assurance of scientific integrity with regard to the use of the data. COPD Gene data can be accessed through dbGaP and also can be directly accessed through collaboration with COPD Gene investigators. An institution, company or investigator who seeks access to the COPD Gene data directly from the COPD Gene Investigators will be required to agree to the following:

1. All data (genetic, imaging and phenotype) obtained from COPD Gene will be used in a manner that protects the privacy and confidentiality of the participant subjects. No attempt will be made to identify subjects or link data to personal information that is readily identifiable or to contact COPD Gene subjects in relationship to genetic, imaging or phenotype data.
2. Analysis of the COPD Gene data will be limited to conformance with the consent groups for genetic studies. Some COPD Gene subjects have agreed to allow use of their genetic information into any disease, while others limited their sample use to smoking-related disorders.
3. The data will not be distributed to other individuals without approval from COPD Gene.
4. The data will be treated confidentially, physically secured, and will not be directly accessible from the internet. Authorized users will adhere to information technology practices in all aspects of data management to assure that only authorized individuals can gain access to the COPD Gene data sets.
5. The data must be destroyed if requested by the COPD Gene Executive Committee. It is understood that this applies to the original COPD Gene data; it does not apply to new, appropriately de-identified data that may be generated.
6. The COPD Gene Executive Committee will be notified within twenty-four (24) hours of the user becoming aware that there has been any unauthorized data sharing, breaches of data security, or inadvertent data releases that may compromise data confidentiality.
7. Manuscripts resulting from COPD Gene data must be submitted for approval by the COPD Gene Executive Committee prior to publication or presentation at public meetings.
8. The COPD Gene data, in whole or in part, may not be sold to any individual at any point in time for any purpose.
9. An investigator may not move the COPD Gene data from one institution or company to another, in whole or in part, without the written approval of the COPD Gene Executive Committee.

10. Use of COPDGene data on portable media, such as a CD, flash drive, or laptop, is discouraged. A limited data set (containing subject identifiers) must be encrypted when stored on a portable device.

Data Request Form

Send Data Request Form to: [name], PhD, Associate Director of COPD Gene: [contact]

* The costs associated with the transfer of data are the responsibility of the requestor. Cost estimates can be provided prior to submission of the proposal.

Investigator: _____

Date: _____

Title of Ancillary Study: _____

Ancillary Study Number: _____

Smoking-related disease study Other Disease(s) not related to smoking

Subject Selection (check one or more)

Final Analysis Primary 10,300

Exclusionary Disease: ILD & Bronchiectasis (n=64)

Or Specific GOLD classification

GOLD 0 – Smoker Controls (n=4388)

GOLD 1 (n=794)

GOLD 2 (n=1922)

GOLD 3 (n=1162)

GOLD 4 (n=606)

GOLD Unclassified (n=1257)

Nonsmoker Normals (n=108)

Match predefined subject list (attach .csv, .xls, etc.)

Custom criteria (ex. “if percent Emphysema > 40%”) Specify in Additional Comments.

Output File Format

SAS JMP Tab-delimited TXT

Phenotypic Data

Visit 1 Phenotype data

Genetic Data

- COPD Gene GWAS, PLINK format (9970 subjects, file size= 1.5GB)
- GWAS with Imputed Data, PLINK format (9970 subjects, file size=138.5 GB)
- Exome Chip (2313 subjects, file size=145 MB)
- Exome Sequencing

To reduce file size on GWAS or Imputed data, you can request specific SNPs and/or chromosomes:

Specific Chromosome _____

Specific SNPs and/or region _____

Imaging Data

- CT Scans (file size approx.. 0.3 GB per subject/series/reconstruction)
 - Inspiratory Standard Reconstruction
 - Expiratory Sharp Reconstruction

Quantitative Data

- Lung volume, Percent below thresholds, Mean attenuation (Histo)
- Lobar data, as above
- Airway measurements- Inspiratory only, unless Expiratory is specified (limited)(
- LAC

Additional Requests/Comments:

All data to be sent will be de-identified unless a limited dataset request has been approved and data use agreements are signed.

Request for a Limited Data Set (containing subject identifiers/dates)		
	IRB Approved Protocol	Data Use Agreement

Genetic Data		
Imaging Data		
Phenotypic Data		

Method of data transfer: Total size of files will impact possible methods. Total size < 8 GB can be transferred via secure SFTP. *CT scans will require the requestor to supply a portable hard drive.*

Name and Email Address for Data Recipients: _____ _____ _____
--

Data Access
Investigator Certification Form
Required prior to transfer of data.

Title of Study: _____
Ancillary Study Number _____ (assigned by COPDGene)
Principal Investigator: _____

COPDGene and _____ (Name of Principal Investigator) hereby enter into this Distribution Agreement.

Investigator: _____, whose principal affiliation is with _____, requests access to Study Data and/or Materials.

Confidentiality and Privacy of Subjects

I certify that all data (genetic, imaging, phenotypic) obtained from COPDGene will be used in a manner that protects the privacy and confidentiality of the participant subjects. No attempt will be made to identify subjects, to link specimens or data to personal information that is readily identifiable, or to contact COPDGene subjects in relation to the specimens, CT images or data.

Restricted Use of Data

I certify that all data obtained from COPDGene will be used for research purposes only, at this institution only, and only for the analyses described in this request. Also, the data will not be allowed to come into the possession of any other persons except those engaged in research under my direct supervision who accept these restrictions.

This Agreement is not transferable. Recipient agrees that substantive changes made to the Research Project described above, and/or appointment by Recipient of another Investigator to complete the Research Project, require execution of a new Agreement in which the new Investigator and/or new Research Project are designated.

Publications and Acknowledgement of COPDGene Support

I agree to follow the COPDGene Publications Policies and Procedures for publications incorporating data arising from use of the COPDGene database and to acknowledge COPDGene in all publications and presentations of studies utilizing data from COPDGene.

Recipient's Resulting Data to be Provided to COPDGene DCC

I agree to provide newly created analytic variables derived from the COPDGene data set to the COPDGene DCC for incorporation into the general data set. Use of new Data generated solely by the Research Project from Data distributed by COPDGene will be restricted for use by the Collaborating Investigator for 12 months after the completion of the Research Project unless other arrangements are mutually agreed upon. After 12 months, the Data generated by the Research Project will be available to all COPDGene Investigators. The COPDGene Investigator(s) agree to acknowledge the contribution of the Collaborating Investigator(s) who generated the Data from the Research Project in any and all oral and written presentations, disclosures, and publications resulting from any and all analyses of Data generated by the Research Project under this agreement. The COPDGene Investigator will acknowledge Collaborating Investigator(s) as co-authors, as appropriate, on any publication.

Reporting Requirements

Recipient agrees to provide an annual report to COPDGene using the Ancillary Study Investigator Annual Progress Report Form.

Protection of Limited Data Sets

I certify that all limited data sets obtained from COPDGene will be properly stored, encrypted and password protected at all times and deleted after the analyses described in this request have been completed.

Requesting Investigator

Signature by the Requesting Investigator is documentation of agreement with Items 1 through 6 above.	
Signature:	Date:
Printed Name:	
Title:	
Telephone:	
E-mail address:	

